## **5. Study Drug(s):**

As described in section 1.2, losartan potassium is an FDA-approved drug for the treatment of hypertension, left ventricular hypertrophy and diabetic nephropathy. It is prescribed for oral intake at doses from 25-100 mg per day with a usual starting dose of 50 mg per day which is what will be used for this study. Losartan potassium was developed by Merck under the proprietary name Cozaar® and is now generically available.

Prior to starting the study medication, a study physician will review the effects of losartan, its side-effects and how the medication should be taken with all subjects. At this time, the physician will answer any questions the subject has regarding the study medication. Subjects will be evaluated weekly while they are taking the medication. Blood work will be repeated 2, 4 and 6 weeks after randomization to identify any clinically relevant abnormalities.

Following randomization, subjects will begin a closed label course of 50mg of Losartan daily for 4 weeks or placebo for the same duration of time. Losartan will be initiated within 7 days of injury after initial tests are performed and any abnormalities are ruled out. No initial dosage adjustment is necessary. The drug will be self-administered by the subject with or without food and will be ingested once a day. With the dose that will be used in this study, no tapering is necessary at the end of the intervention phase or if the subject needs to be withdrawn from the study.

### **5.1 Study drug compliance/adherence**

During the weekly patient encounters, a member of the research team will answer any questions the subject might have about the medication, will assess and promote medication adherence and monitor any side effects that the patient might be experiencing. The subject will be instructed to bring the medication so that pill counting can be performed as a measure to assess adherence. Also, at the time of randomization and at each weekly encounter, the subject will be given a medication log to complete. The medication log will allow the patient to record the day and time of day the study medication and any concomitant medications were taken during that time period.

The medication log will become part of the research records, but will not be placed in the medical record. A statement will be placed in the electronic medical record of the subject stating the subject is enrolled in a double-blinded placebo controlled trial using losartan potassium as an investigational drug. In the event of a medical emergency, a health care provider can contact the study Medical Director or designated study investigator to obtain information about the assigned study drug during the dosing period.

### **5.1.1 Withdrawal of subjects due to non-compliance/adherence**

Because we are interested in evaluating efficacy, we will use a per-protocol approach, as opposed to an intention-to-treat approach for the conduct of this study. As such, subjects that are non-compliant with the medication regimen (defined as taking less than 80% of the medication doses) will be withdrawn from the study and additional subjects will be recruited to replace subjects that have been withdrawn due to non-compliance. Subjects that are withdrawn for non-compliance will be instructed to terminate administration of the study medication without tapering down the dose and to return unused medication to the investigators.

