The severity of an adverse event will be determined by the study medical director based on the criteria stated in section 8.1. Additionally, the medical director will assign the event a grade of mild, moderate, or severe. If it becomes medically necessary to withdraw the subject from the study, the study medication will be discontinued. The subject will be followed clinically until the adverse event or abnormal test findings felt to be associated with the study drug resolves or stabilizes at a level acceptable to the Sponsor-Investigator. This follow-up will include assessment of vital signs, physical examination and assessment of blood work. Follow-up blood work will be performed 4-6 weeks ( $\pm 3$  days) after discontinuing medication to ensure that lab values have returned to normal ranges after discontinuation of the study medication. The subject will be treated for any medication related problems as clinically appropriate. Information from this appointment will be documented in the subject's case file. The patient will be terminated from the study, and will not complete any further follow-up appointments for the study. Subjects that are terminated from participation in the study due to an adverse event will be replaced by recruitment of another subject.

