## **9.3        Definition(s): Analysis population(s)**

All analyses for treatment group comparisons will use the original treatment assignment as randomized for each participant (intent-to-treat) regardless of the subject's actual compliance with taking the study medications. Secondary analyses will consider per protocol analysis, in which compliance with the study medication regimen will be defined as taking greater than 80% of the doses.

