### **13. Study Discontinuation Criteria:**

#### **13.1 Discontinuation of individual research subjects (refer also to sections 5.1.1 and 8.4)**

Because we are interested in evaluating efficacy, we will use a per-protocol approach, as opposed to an intention-to-treat approach for the conduct of this study. As such, subjects that are non-compliant with the medication regimen (defined as taking less than 80% of the medication doses) will be withdrawn from the study and additional subjects will be recruited to replace subjects that have been withdrawn due to non-compliance. Subjects that are withdrawn for non-compliance will be instructed to terminate administration of the study medication without tapering down the dose and to return unused medication to the investigators.

As specified in section 8.4 subjects with symptomatic hypotension or abnormal lab values will be withdrawn from study participation. Additionally, females that become pregnant while taking the study medication will immediately stop the medication and will be withdrawn from the study. These withdrawn subjects will be followed clinically based on standards of care until the adverse event or abnormal test findings felt to be associated with the study drug resolve or stabilize at a level satisfactory to the Sponsor-Investigator, however no further research data will be collected once the subject has been withdrawn.

Subjects that are withdrawn due to non-compliance with the study medication, symptomatic hypotension, abnormal lab values or pregnancy will be reported as an adverse event. Withdrawn subjects will be replaced by recruiting another subject to take the place of the withdrawn subject.

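### Sections 5.1.1, 8.4 and 13.1 withdraw and replace randomised subjects and end their outcome data, so the intention-to-treat comparison that section 9.3 requires cannot be carried out for the later endpoints

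*Combined protocol and SAP*

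**What the plan says.** Section 5.1.1, repeated in section 13.1, gives an interest in efficacy as the reason that "we will use a per-protocol approach, as opposed to an intention-to-treat approach for the conduct of this study". Subjects taking less than 80% of doses "will be withdrawn from the study and additional subjects will be recruited to replace subjects that have been withdrawn due to non-compliance".

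Section 8.4 deals with safety withdrawals: symptomatic hypotension, abnormal laboratory values, pregnancy after enrolment, and adverse events that make withdrawal medically necessary. After such a withdrawal, "The patient will be terminated from the study, and will not complete any further follow-up appointments for the study". Also, "Subjects that are terminated from participation in the study due to an adverse event will be replaced by recruitment of another subject". Section 13.1 provides clinical follow-up of subjects withdrawn for hypotension, laboratory values or pregnancy, "however no further research data will be collected once the subject has been withdrawn". It closes with a general rule: "Withdrawn subjects will be replaced by recruiting another subject to take the place of the withdrawn subject".

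Section 9.3 points the other way: "All analyses for treatment group comparisons will use the original treatment assignment as randomized for each participant (intent-to-treat"), whatever the subject's actual compliance. A per-protocol analysis is secondary, and for it "compliance with the study medication regimen will be defined as taking greater than 80% of the doses".

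Section 9.4 expects less than 5% loss at 6 months and 10-15% at 12 months, and concludes that only recurrence could be appreciably affected. Section 4 sets total enrolment at 20 and counts a subject as enrolled from consent.

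**The concern.** One part of the protocol rejects by name the analysis principle that another part requires. Harmonising the labels would not be enough, because the conduct rules decide which data exist. Outcomes that are never collected cannot be restored at analysis.

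Besides safety, the trial's stated purpose is pilot data on effect size and variability for a later trial (sections 1.2, 2.1 and 9.2). Non-adherence, hypotension and abnormal laboratory values all arise after randomisation and may depend on treatment. If such subjects have no later outcomes and others take their places, the effectiveness estimates describe mainly subjects who adhered to and tolerated treatment, while section 9.3 calls them intention-to-treat. A later sample-size calculation would inherit that mismatch.

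**Working it through.** **Inputs.** Dosing is once daily for 4 weeks, so 28 doses (sections 5 and 6.3). The Aim 2 primary endpoints are flexibility and isokinetic torque at 6 weeks and 6 months, and fibrosis on MRI at 6 months (section 9.1.1). Recurrence is followed for 12 months. The sample is 20, 10 per group (section 9.2). It is an approved number with no alpha, power or effect size behind it, so there is no calculation to reproduce.

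**Step 1: the rules side by side.**

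| Reason for withdrawal | Source | Outcome data afterwards | Replaced |
|---|---|---|---|
| Less than 80% of doses | 5.1.1, 13.1 | None, implied by withdrawal from the study | Yes |
| Symptomatic hypotension, abnormal laboratory values, pregnancy | 8.4, 13.1 | None, stated in 13.1 | Yes |
| Adverse event making withdrawal medically necessary | 8.4 | No further study appointments, stated | Yes |

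Section 9.3 keeps every one of these randomised subjects in the main comparison. A subject withdrawn during dosing contributes baseline and early weekly data, but no Aim 2 primary endpoint. Return-to-sport and recurrence data are truncated.

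**Step 2: what separates the two analysis sets in section 9.3.** The cut is 0.80 × 28 = 22.4 doses, so no whole count falls on exactly 80%: 22/28 = 78.6% leads to withdrawal and 23/28 = 82.1% is per-protocol. For withdrawals under 5.1.1, the intention-to-treat and per-protocol analyses therefore rest on the same observed 6-week and 6-month data.

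**Step 3: the loss forecast.** With replacement, the number randomised is 20 plus the number withdrawn. If withdrawals count as loss (an assumption):
- one withdrawal: 1/21 = 4.8%, just within <5%
- two withdrawals: 2/22 = 9.1%, above it

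Section 9.4 does not mention these withdrawals. The totals of 21 and 22 also exceed the 20 fixed in section 4.

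**Step 4: what the good/poor-score analysis in section 9.4 can do.** Suppose k subjects per arm are unobserved and each is replaced in the same arm. The documents do not state this; section 3.2 uses sequentially numbered envelopes. The best-to-worst bounds on the recurrence risk difference are then 2k/(10 + k) wide:
- k = 1: 2/11 = 18 points
- k = 2: 4/12 = 33 points

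For scale, with 10 per arm and 50% recurrence in each, the 95% sampling interval has half-width 1.96 × √(0.5/10) = 0.44, so it is about 88 points wide.

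**Step 5: possible bias in a mean difference.** Assume that withdrawal removes the lowest share w of an arm on a normally distributed trait whose correlation with the outcome is r. The mean of those remaining shifts by r·φ(z_w)/(1 − w) SD, which is 0.350r at w = 0.2 and 0.195r at w = 0.1. The difference between arms is 0.155r. For r = 0.3 to 0.5 that is 0.05 to 0.08 SD. If both arms lose similar subjects equally, it is about zero. The standard error with 10 observed per arm is √(2/10) = 0.45 SD.

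**The case against.** The strongest defence is that 5.1.1 and 13.1 govern conduct and 9.3 governs analysis. It fails: 5.1.1 and 13.1 reject intention-to-treat by name, and the conduct rules remove the data that the analysis needs.

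Other objections stand and limit the point.

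- A reader might infer that the two analysis sets become identical. They do not. The mixed models in section 9.4 can use the early visits of withdrawn subjects, the good/poor-score analysis assigns them values, and their safety data are kept. A subject withdrawn for a week-6 laboratory value may have taken all 28 doses, and so be in the per-protocol set without 6-month data.
- A reader might infer that any adverse event leads to withdrawal. Section 8.4 limits this to medical necessity, and section 13.1 names specific triggers.
- For non-adherent subjects, the end of data collection is implied, not stated. The sentence in 13.1 about research data refers to safety withdrawals.
- The trial is small and disclaims power, no withdrawal rate is documented, and the number affected could be zero. But estimation is a stated purpose, so low power does not excuse uncollected outcomes.
- Preferring intention-to-treat over the sponsor's interest in efficacy is partly a judgement. It is also the choice section 9.3 already makes, and the secondary per-protocol analysis serves the other interest.

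**Conclusion.** The contradiction is real and should be resolved. Following the protocol as written gives a comparison labelled intention-to-treat that lacks the 6-week and 6-month outcomes of subjects withdrawn during dosing, and section 9.4 does not allow for that loss.

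The conclusion rests on the text and on the uncollected outcomes, not on a demonstrated bias. A reader might infer that the effect estimates would be materially distorted. The documents do not support this: the modelled shift of 0.05 to 0.08 SD depends on assumed correlations and withdrawal shares and is small beside a standard error of 0.45 SD. The recurrence bounds of 18 or 33 points are likewise well inside sampling uncertainty.

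Nor is the safety aim undermined. Events up to withdrawal are recorded by arm, and clinical and laboratory follow-up continues after safety withdrawals, so Aim 1 is largely preserved.

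**What to change.** 1. Reconcile 5.1.1, 8.4 and 13.1 with 9.3 by separating stopping study drug from leaving the study. Every randomised subject, on or off drug, is asked to complete the outcome visits and calls already in Table 1, unless consent is withdrawn or the investigator judges an assessment unsafe. The sentences in 8.4 and 13.1 that end appointments and research data need to be revised accordingly.
2. Delete the per-protocol sentence from 5.1.1 and 13.1, and analyse every randomised subject as randomised. In the analysis, adherence defines only the secondary per-protocol set. Whether low adherence still leads to stopping study drug is for the sponsor to settle when reconciling these sections; no clinical stopping rule is proposed here.
3. If replacement is kept, include both the replaced subject and the replacement in the intention-to-treat set, and restate the totals in sections 4 and 9.2.
4. Correct the loss statement in 9.4 so that it counts withdrawals made under the protocol's own rules.

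Changing 9.3 to per-protocol instead would remove the contradiction but leave the outcomes uncollected.

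The cost is a protocol amendment, revised consent wording, and follow-up of a few off-drug subjects at assessments already scheduled. If replacement is kept, more than 20 subjects are randomised and followed. Including non-adherent subjects may dilute the estimated effect.

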## **5.2 Study drug supplies**

### **5.2.1 Formulation and packaging**

Losartan will be ordered through HC central pharmacy and billed to the study. The UPMC Investigational Drug Service will provide the Losartan or placebo. The placebo will be formulated to have the same appearance as the Losartan. Study medications will be provided to the subjects free of charge.

### **5.2.2 Preparing and dispensing**

IDS will blind the IP and matching placebo. The IDS will dispense per physician order.

### **5.2.3 Drug administration**

The drug is self-administered orally with or without food and will be ingested once a day as per protocol

## **5.4 Study drug storage and accountability**

The IDS will store IP under controlled room temperature which is monitored daily and will maintain accountability records. Upon completion of the study or expiration of the medication, destruction will occur per IDS policy #103.

## **5.5 Concomitant Medications**

At the time of randomization and at each weekly encounter with the study staff, the subject will be given a medication log to complete. The medication log will allow the patient to record the times/days the study medication and any concomitant medications taken during that time period. During the review of the log, the study staff will ask and document questions about concomitant medications and the reasons for taking them. Adverse events related to concomitant medications will be recorded.

### **5.5.2 Rescue Medication**

## **6. Research Study Procedures:**

### **6.1 Recruitment Procedures**

This prospective randomized phase 1 trial is a joint effort of the UPMC Center for Sports Medicine/University of Pittsburgh and the Department of Orthopaedics and Rehabilitation at BAMC.

Subjects recruited through the UPMC Center for Sports Medicine will be informed of and referred to the study by their athletic trainer and/or physician. With permission of the subject, a research assistant will then contact them and initiate the study process. Alternatively, potential subjects will sign a Health Insurance Portability and Accountability Act (HIPAA) authorization for sharing of contact information, which will be forwarded to the study coordinator, who will in turn contact the subject to provide additional information concerning the study.

Subjects recruited through the Department of Orthopaedics and Rehabilitation at Brooke Army Medical Center (BAMC) in San Antonio, Texas that meet the inclusion criteria (grade II/III hamstring strains due to sports or duty related injury) will be referred to the Research Coordinator in the BAMC Department of Orthopaedics and Rehabilitation for possible recruitment. All testing and evaluation of recruited subjects will be conducted at the Center for the Intrepid in the Department of Orthopaedics and Rehabilitation at BAMC,

MRI's will be performed at the BAMC Department of Orthopaedics and Rehabilitation MRI Clinic.

## 6.2 Informed Consent Process

The Research Coordinator will explain the details of the study, including the purpose of the study, procedures that will be utilized and the associated risks and benefits. Potential subjects will be assured that the decision of whether or not to participate in this study will not have any effect on their care. All questions that the subject may have prior to signing the informed consent form will be answered to the subject's satisfaction by one of the investigators. If the subject is willing to participate in the study, the subject will sign an informed consent form that has been approved by the University of Pittsburgh Institutional Review Board (for subjects recruited at the UPMC Center for Sports Medicine) or by the BAMC-IRB (for subjects recruited at Brooke Army Medical Center) prior to participating in any research-related activities.

## 6.3 Screening procedures

### 6.3.1 Baseline Demographics and Activity Level

Demographic information that will be recorded include age, sex, weight, height, body mass index (BMI), education level, sports and work activity level, smoking history and marital status.

**Sports Activity** - We will use the sports activity rating scale developed by Marx et al. to measure the subject's level of sports activity in the year prior to injury. This scale consists of 4 questions (running, cutting, decelerating and pivoting) that are rated in terms of the frequency with which the subject performed the activity (less than once per month, once per month, once per week, 2 or 3 times per week or 4 or more times per week) in the prior year. Test retest reliability for this scale over a two-week period was high (ICC=0.97) and it had moderately strong correlations with the Cincinnati and Lyhsolm scores.

**Work Activity** - Work activity will be measured with the Occupational Rating Scale of the Cincinnati Knee Rating System^70. This is a patient-reported measure of work activity in which individuals will report the duration or frequency of sitting, standing and walking, walking on uneven ground, squatting, climbing, lifting and carrying as well as the amount of weight that they carry while at work. Each item is scored on a scale that ranges either from 0 to 5 or 0 to 10 such that higher scores indicate less sedentary activity and more physically demanding work activity. The item scores are summed and multiplied by 2 to create a score that ranges from 0 to 100. Cincinnati Occupational Rating Scale has demonstrated high test-retest reliability in both patients (ICC=.97) and uninjured subjects (ICC=.87).

### 6.3.2 Baseline Assessment of Injury

At the time of study enrollment, the subject will be interviewed about the mechanism of injury (movement that was made during injury), presence or absence previous symptoms at the injury site, presence or absence of ecchymosis and the ability to walk and run. An examination will include inspection to confirm the presence or absence of ecchymosis. Palpation of the posterior thigh will be performed with the subject in prone and the knee extended. The point of greatest pain will be marked and the distance to the ischial tuberosity will be measured and the presence or absence of a palpable defect will be recorded. Pain during resisted knee flexion will be graded on an 11 point (0 to 10) numerical pain rating scale.

Subjects will be eligible for participation in the study if the physical examination reveals: 1) localized tenderness with or without a palpable defect; 2) pain and weakness with resisted knee flexion with the individual in the prone position and 3) pain and a limitation (in comparison to the contralateral leg) in the popliteal angle with the hip at 90 degrees of flexion. Presence of a grade II/III hamstring strain will be confirmed on the baseline MRI that is performed prior to randomization. MRI evidence of a grade II/III hamstring strain includes edema with architectural disruption indicating a partial tear (grade II) or edema with complete rupture of the muscle or tendon (grade III). Excellent intra- and inter-rater reliability has been reported for this MRI grading system of acute hamstring injuries.

### 6.3.3 Baseline Vital Signs, Medical History and Physical Examination

Blood pressure will measured according to the American Heart Association Guidelines. The subject will be comfortably seated, with his legs uncrossed. The cuff will be placed on the upper arm that will be at the level of the midpoint of the sternum and all measurements will be performed with an aneroid sphygmomanometer. For the initial visit, measurements will be performed in both upper extremities. The midline of the bladder of the cuff will be placed over the brachial artery. The stethoscope will be placed over the brachial artery but in the antecubital fossa. The cuff will then be inflated until the brachial artery is occluded (usually until 30 mm Hg above the point at which the radial pulse disappears). The cuff is then deflated and the first and last sounds should be the systolic and diastolic pressures.

We will also measure orthostatic blood pressure using procedures described by the Centers for Disease Control. After lying in the supine position for 5 minutes, heart rate and blood pressure will be measured using the procedure described in the paragraph above. Following this, the subject will stand and blood pressure and heart rate will be measured again after 1 and 3 minutes. A drop in systolic pressure greater than or equal to 20 mm Hg or a drop in diastolic blood pressure greater than or equal to 10 mm Hg or reports of lightheadedness or dizziness would be considered abnormal. Individuals with orthostatic hypotension will be excluded from further participation in the study.

A medical history, review of systems and physical examination will be performed for all subjects during screening. The medical history will include a review of the chief complaint, history of present injury, past medical history, allergies, medications, and social and family history.

